### **APPLICATION FOR APPROVAL FOR USE OF HUMAN PARTICIPANTS IN RESEARCH**

Before completing this application, please read the [Application Instructions](#) and [Policies and Procedures for Human Research Protections](#) to understand the responsibilities for which you are accountable as an investigator in conducting research with human participants. The document, *Application Instructions*, provides additional assistance in preparing this submission.

***Incomplete applications will be returned to the investigator. You may complete this application online and save it as a Word document.***

***If this research is related to a grant, contract proposal or dissertation, a copy of the full grant/contract proposal/dissertation must accompany this application.***

**Please carefully edit and proof read before submitting the application. Applications that are not filled out completely and/or have any missing or incorrect information will be returned to the Principal Investigator.**

### **REQUIRED TRAINING FOR RESEARCH INVOLVING HUMAN SUBJECTS**

Under the direction of the [Office of the Vice Provost for Research](#), Northeastern University is now requiring completion of the NIH Office of Extramural Research training for all human subject research, regardless of whether or not investigators have received funding to support their project. ***This requirement will be effective as of November 15, 2008 for all new protocols.***

If you have not yet completed some type of human subject protection training, Northeastern University now has an account with CITI for Human Subjects Training, which can be accessed at the following url:

<https://www.citiprogram.org>. Once you are on the site, click the “Register” button located on the top right of the page to begin. All NU-affiliates can take the CITI training course at no charge. **Please register using your NU email address and then complete the CITI Social & Behavioral Research Stage 1 Basic Course.**

**Principal Investigators, student researchers and key personnel (participants who contribute substantively to the scientific development or execution of a project) must include a copy of their certificate of completion for this web-based tutorial with the protocol submission.**

\*\*\*\*\*

\*\*\*\*\*

- Certificate(s) Attached
- Certificate(s) submitted previously – on file with the NU’s Office of Human Subject Research Protection

## B. Protocol Information

Title: Daily Activity Study of Health (DASH) \_\_\_\_\_

Projected # subjects 80

Approx. begin date of project 06/01/2019

Approx. end date 06/30/2021

month,

day, year

month, day, year

It is the policy of Northeastern University that no activity involving human subjects be undertaken until those activities have been reviewed and approved by the University's Institutional Review Board (IRB).

- **Anticipated funding agency/source for project (or none)** NIH/NIA
- \_\_\_\_\_
- **Has/will this proposal been/be submitted through:**
  - NU's Office of Research Administration and Finance (RAF) x
  - Provost \_\_\_\_\_
  - Corp & Foundations \_\_\_\_\_
  - Other \_\_\_\_\_
- **Grant Title: Changing and understanding motivation to increase physical activity among sedentary older adults** \_\_\_\_\_
- **Grant ID:** ePAWS# 10002361
- \_\_\_\_\_

C.

Will Participants Be:	Yes	No	Does the Project Involve:	Yes	No
Children (<18)	_____	x	Blood Removal?	_____	x
Northeastern University Students?	_____	x	Investigational drug/device?	_____	x
Institutionalized persons?	_____	x	Audiotapes/videotapes?	_____	x
Prisoners?	_____	x			
Cognitively Impaired Persons?	_____	x			
Non or Limited English Speaking Persons?	_____	x			
People Living outside the USA?	_____	x			
Pregnant Women/Fetuses?	_____	x			
Other? (Please provide detail)	_____				

***Please answer each of the following questions using non-technical language. Missing or incomplete answers will delay your review while we request the information.***

**D. What are the goals of this research? Please state your research question(s) and related hypotheses.**

This multidisciplinary pilot proposal focuses on examining the efficacy of factors that have shown promise in motivating sedentary older adults to become more physically active as well as

to investigate changes in patterns of activation of the neural networks, as indexed by MRI and fMRI, that support these factors and changes in physical activity.

**Aim 1:** Our primary aim is to assess, in a six-week pilot randomized controlled trial with healthy but sedentary older adults, the efficacy of self-affirmation + gain-framed messaging versus a control group that receives loss-framed messaging only on changes in physical activity. We will also examine whether any differential physical activity engendered in the two groups is maintained at 3 months post-intervention.

**Exploratory Aim 2:** A secondary exploratory aim will examine the extent to which individual differences in motivation, conscientiousness, growth mindset and other factors moderate the effects of our intervention on physical activity change, for our self-affirmation + gain-framed messaging versus a control group that receives loss-framed messaging only, over the course of the intervention and at 3 months post-intervention.

**Exploratory Aim 3:** Another exploratory aim will examine the extent to which our intervention influences patterns of activation and connectivity in self-referential brain networks including medial prefrontal cortex and ventral striatum that have been related to self-affirmation of health messages (Falk et al, 2015; Gutchess et al., 2007), as well as other networks associated with aging and physical activity (e.g. resting state executive control, default and salience networks), and whether activation and connectivity within and between these networks is associated with physical activity change both following the intervention and 3 months post-intervention.

We believe that our intervention will provide valuable, novel information about the efficacy of promising factors to enhance physical activity, and in turn cognitive and brain health, in sedentary older adults as well as the functional brain changes and individual differences that support these potential changes in physical activity.

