## RESEARCH ACTIVITIES:

### Overview:

There will be a total of --- visits, with each visit split into multiple sessions. Participants will complete neuropsychological and behavioral inventories, cognitive tests, writing tasks, and computer tasks at these visits. There will also be 2 visits, one before intervention and one after dedicated to physical assessments. Additionally, participants opting into the MRIs will come in-person before and after intervention for the MRI. Outside of the sessions, participants will wear two accelerometry devices for 4 separate weeks in the study and receive and respond to daily messages as part of the intervention. Each of these aspects and what they entail is detailed below.

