#### Accelerometry:

Participants will be fitted with two accelerometers and have their cardiorespiratory status estimated. The estimation uses a regression equation that includes age, sex, body mass index, and resting heart rate. We will obtain a non-exercise CRF estimation before and after the six-week intervention. To perform the CRF estimation, which will be remote, we will ask participants to report their supine resting heart rate (i.e., the average of all R-R intervals over ten seconds) after they have rested quietly for ten minutes. Participants will also complete a physical assessment focused on their basic walking speed, their ability to transition repeatedly from sitting to standing, and their balance.

Accelerometers, chargers, and related materials will be sent to participants through the mail after the consent meeting and will be returned after the 3-month follow-up session. Accelerometry data will be recorded during wakefulness and sleep, with the exception of bathing or swimming, for the week between the Red and Orange visits (before the intervention begins; i.e., baseline), for two separate weeks during the 6-week intervention (with additional days during this timeframe for any participant who does not wear the devices consistently during the original period), and for a week after the 3-month follow-up visit. This will characterize change in physical activity from baseline and maintenance. It will be assessed using two accelerometers worn simultaneously. The first is a wrist-worn tri-axial accelerometer (ActiGraph GT3X Link, Pensacola, FL). This accelerometry data will be downloaded in 60-second epochs (ActiLife software, ActiGraph, Pensacola, FL) and will be screened for wear time using standard methods (Choi et al., 2011). The second device is a tri-axial accelerometer and inclinometer (activPAL) and will be worn on the thigh using an adhesive.

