The data are stored on a Heroku server. Heroku’s privacy policy states that, “We take steps to protect the privacy of our customers and protect data stored within the platform. Some of the protections... include authentication, access controls, data transport encryption, HTTPS support for customer applications, and the ability for customers to encrypt stored data.” Further, answers to survey questions are stored in number form corresponding to the multiple-choice option selected, without a key to the meaning of the choice or the question itself. There is a mandatory Administrator login, requiring a username and password, to gain access to this data. Only necessary research personnel will have the login information.

We will use the Remind app to deliver links to the oTree survey via text to participants every day. Remind is a texting service primarily used by educators, students, and parents that is compliant with federal privacy laws protecting students. It has been awarded the ISO 27001:2013 certification, which is an international standard for information security

management and governance (<https://www.remind.com/blog/iso-27001-certification>). Participants will not discuss personal and/or health information through Remind, and the links sent to them will not contain private information.

Follow-up measures:

After the intervention, participants opting into the MRIs will undergo repeat neuroimaging (i.e., resting state MRI, structural MRI, task fMRI, DWI), physical assessment session, and specified cognitive tests. Additionally, in an attempt to determine the extent of benefits following the end of the formal intervention, participants will be assessed again at 3 months post-intervention, with 7 days of accelerometry recording to determine physical activity, and behavioral and psychosocial measures to assess continued cognitive benefits.

Outcome measures outside of the neuropsychological assessment battery are as follows:

Outcome measure	Type	Timeframe	Brief description
Total step count (average steps/day)	Primary	Week 0 (baseline); Week 3; Week 6; 3 Months	This metric quantifies the change in the average number of steps taken each day, from the baseline, Week 2, Week 6, and 3-month periods. It is a marker of change in habitual ambulatory activity.

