Sedentary behavior (average min/day)	Primary	Week 0 (baseline); Week 3; Week 6; 3 Months	This metric quantifies the change in the average amount of time spent sedentary each day, from the baseline, Week 2, Week 6, and 3-month periods. It is a marker of time spent inactive.
Moderate-vigorous activity (average min/day)	Secondary	Week 0 (baseline); Week 3; Week 6; 3 Months	This metric quantifies the change in the average amount of time spent engaged in moderate-to- vigorous physical activity each day,

			from the baseline, Week 2, Week 6, and 3-month periods. It is a marker of physical activity.
Walking Cadence	Secondary	Week 0 (baseline); Week 3; Week 6; 3 Months	This metric reflects the participant's average steps per minute. We will examine change from baseline over the course of the intervention and follow-up.
Walking Bouts	Secondary	Week 0 (baseline); Week 3; Week 6; 3 Months	This measures the number of 'bouts' of physical activity (in our case, steps). We will have two counts: the number of 5+ minute bouts and the number of 10+ minute bouts of walking. We will examine change from baseline over the course of the intervention and follow-up.

A spreadsheet holding the list of neuropsychological assessments to be used, with brief descriptions, is attached. They will be administered at T1 (Week 0), T2 (Week 1), T3 (Week 6), and/or T4 (3 Months).

		6 weeks of daily messages								
(soon after phone screen)	Week 0/ Start	1	2	3	4	5	6	7	14/ 3 months	15
	(shipping)	Devices			Devices			Devices	>>>	Devices
Consent Visit	Visit 1	Visit 2		Phone Reminder			Visit 3	Phone Reminder	Visit 4	Debrief
Remote Visit	Remote Visit	Remote Visit					Remote Visit	Phone Reminder	Remote Visit	Debrief
		Optional MRI					Optional MRI			

Who will conduct the experimental procedures, questionnaires, etc.? Where will this be done? *Attach copies of all questionnaires, interview questions, tests, survey instruments, links to online surveys, etc.*

Most research activities are remote and will be completed by participants in their homes. Optional MRIs occur in the Center for Cognitive & Brain Health in the ISEC on the Northeastern University Boston campus. As indicated above, all experimental procedures will be implemented and monitored by trained staff in the Lab. All questionnaires, surveys, etc. are attached.

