**N. Benefits**

What benefits can the participant reasonably expect from his/her involvement in the research? If none, state that. What are potential benefits to others?

There is the potential for direct benefit to participants randomized to the self-affirmation + gain-framed health messaging arm of the study. Participants may experience direct benefits from participation such as improved cognition, mood, quality of life, physical fitness or decreased sedentary behavior as a result of participating in the behavioral intervention over a 3-month period. There may be a reduction in central adiposity and cardiovascular benefits. In addition, we are hoping that participants will maintain reductions in sedentary behavior beyond the completion of the study. The findings of this study provide information regarding the effect of simple and cost-effective behavioral intervention in reducing sedentary behavior and improving brain health in a population at risk for cognitive decay. As such, dissemination of this information stands to improve public health.

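### The follow-up promised at three months after the intervention is recorded about 7 to 10 weeks after the last message, and the SAP plans no analysis of it

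*Protocol*

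**What the plan says.** **Protocol.** Section D, Aim 1, asks whether any "differential physical activity engendered in the two groups is maintained at 3 months post-intervention". Exploratory Aims 2 and 3 use the same anchor. The follow-up paragraph in section J says "participants will be assessed again at 3 months post-intervention, with 7 days of accelerometry recording to determine physical activity".

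The timeline table at the end of section J begins at week 0, labelled as the start. It carries the header "6 weeks of daily messages", puts Visit 4 in the column labelled both week 14 and 3 months, and shows device wear in weeks 1, 4, 7 and 15. The line above the table lists "T3 (Week 6), and/or T4 (3 Months" among the assessment times. Under Accelerometry, wear is planned "before the intervention begins; i.e., baseline), for two separate weeks during the 6-week intervention", "and for a week after the 3-month follow-up visit". The Overview likewise has participants "wear two accelerometry devices for 4 separate weeks in the study".

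**SAP.** The wear schedule under Physical activity monitoring lists weeks 0, 3, 6 and 14, the last labelled T5. Other places describe fewer periods:

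- The Abstract has wear before, during and in the last week of the intervention.
- Study timeline names sessions T1 to T4 and three accelerometer calls.
- The compliance paragraph of Physical activity monitoring speaks of three accelerometer weeks.
- The limitations in the Discussion give three one-week periods.

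Study aims contains no maintenance aim. The Analysis plan fits a mixed model with a two-group by three-time interaction and does not list the three times.

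**The concern.** Maintenance is counted from the day the messages stop. If the follow-up result is reported in the words of the aims, readers will take it as persistence about 13 weeks after the last message, when the devices recorded it earlier. The claim about durability would be longer than the data support.

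The second problem is that the SAP does not carry the question through. The protocol lists 3 months as a time point for both primary outcomes and all three secondary outcomes in its table. The SAP mentions the corresponding wear period once, and no model term or contrast uses it.

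**Working it through.** **The plan's own figure.** The SAP sizes the trial on a difference of 10.0 points, SD 14.0, 80% power, two-sided alpha 0.05 and 20% drop-out. An exact two-sample t-test needs 31.76, so 32 completers per arm (power 0.803). Then 32 / (1 − 0.20) = 40 per arm, 80 in total. The figure reproduces. It is tied to a week-4 comparison and does not involve the follow-up.

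**Three months in weeks.** 3 × 365.25 / 12 / 7 = 13.04 weeks.

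**When the messages end.** The table's layout was lost in extraction, so the span of the message bar is uncertain. The header cell sits over week 1, which suggests weeks 1 to 6. The device row, read with the Accelerometry text (baseline wear before the intervention, two wear weeks during it), suggests weeks 2 to 7. Counting to the start or the end of the last message week gives an ending at week 6, 7 or 8.

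| Messages end at week | Gap to Visit 4 (week 14) | Start of week-15 wear | End of week-15 wear | Three months after last message |
|---|---|---|---|---|
| 6 | 14 − 6 = 8 | 15 − 6 = 9 | 16 − 6 = 10 | week 19.0 |
| 7 | 14 − 7 = 7 | 15 − 7 = 8 | 16 − 7 = 9 | week 20.0 |
| 8 | 14 − 8 = 6 | 15 − 8 = 7 | 16 − 8 = 8 | week 21.0 |

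- Visit 4: 6 / 13.04 = 46% to 8 / 13.04 = 61% of three months.
- Device wear: 7 / 13.04 = 54% to 10 / 13.04 = 77%.
- Most generous case, the last day of wear with messages ending at week 6: 13.04 − 10 = 3.04 weeks short.
- Time since start: week 14 is 98 days, and 98 / 30.44 = 3.2 months. The label fits this clock.

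**If the SAP's four-week length is used.** Messages end at week 4 or 5, so week 14 is 14 − 5 = 9 to 14 − 4 = 10 weeks later (69% to 77%). This is still short of three months.

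**The SAP model.** Four wear weeks cannot all be levels of a three-level time factor. The Abstract, Study timeline, the compliance paragraph and the limitations are consistent with baseline, mid-intervention and last intervention week. With those as the three levels, week 14 is outside the model. The only dated group comparison in the SAP is the week-4 one in the power paragraph. Power for a follow-up contrast cannot be computed, because the documents give no effect, SD or retention for it.

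**The case against.** The strongest reply is that the SAP may have dropped the follow-up. It states no maintenance aim, it describes three wear periods in several places, and its references to week 6, week 14 and T5 could be left over from a six-week version. On that view the missing contrast is not a gap, and one stale schedule line remains. This may be so. But the SAP never says that follow-up was dropped, and the protocol still promises it in its aims, overview, accelerometry text, outcome table and calendar. One or the other has to change.

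It can also be said that this is a Stage I pilot, that maintenance is an additional question, and that the outcome table already sets 3 months beside weeks 0, 3 and 6 on study time. This limits the importance of the point but does not reconcile the wording of the aims with the calendar.

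Three stronger readings are tempting and are not supported:

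- A reader might infer that maintenance is measured at about half the stated interval. That describes the remote visit. The activity outcome comes from the devices worn the week after, at 54% to 77%.
- A reader might infer that the three model times are open and could be chosen once the data are seen. They are not listed in the Analysis plan, but the other SAP sections point to one set, and the four-week wear list is the outlier. A reading with changes from baseline at weeks 3, 6 and 14 has no support in the text.
- A reader might take "as a result of participating in the behavioral intervention over a 3-month period" in section N as a third definition of the interval. It is lay wording about benefits and carries little weight.

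**Conclusion.** The contradiction stands. The protocol promises an assessment three months after the intervention, and its calendar delivers device data 7 to 10 weeks after the last message, with the visit at 6 to 8 weeks. No reading of the calendar reaches 13 weeks. In the SAP, the week-14 wear period conflicts with every other description of the wear schedule, and the protocol's maintenance question has no planned analysis.

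This rests on taking the calendar columns as elapsed weeks from start, on three months being 13.04 weeks, and on messages ending somewhere between weeks 6 and 8. The interval finding is firm. The statement about the model is an inference, though the natural one, since the SAP does not name its time points. Neither the 80 participants nor the powered comparison is affected. The point should be corrected before results are reported, because it governs what can be said about maintenance.

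**What to change.** First reconcile, across both documents, the length of the intervention (four or six weeks; the SAP's Figure 2 legend gives 42 days and calls it four weeks) and whether the week-14/15 assessment exists.

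**If it is kept:**

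- In protocol section D and the follow-up paragraph of section J, replace the three-month wording with the actual interval from the last message to device wear.
- In the outcome table, label that point as study time from start.
- Bring the SAP's Abstract, Study timeline, compliance paragraph and limitations into line with its four-week wear schedule, including the session labels (T4 is the three-month visit in the protocol but the end-of-intervention session in the SAP).
- Name baseline, mid-intervention and last intervention week as the three times of the primary model, and leave that model as it is.
- Add one separate secondary contrast: the group difference in change from baseline at the follow-up wear week, intervention minus control, with a 95% confidence interval. Keep it outside the primary group-by-time test. Making follow-up a fourth level would raise that interaction from (2 − 1)(3 − 1) = 2 to (2 − 1)(4 − 1) = 3 degrees of freedom and mix maintenance into the primary question.

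**If it is dropped:** remove week 14 and T5 from the SAP's wear schedule, and withdraw the maintenance question and the three-month time point from protocol sections D and J.

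**Cost.** If kept, the stated follow-up interval becomes shorter and one secondary analysis is added; no new data are needed. If dropped, the trial gives up its maintenance question. The sample size does not change either way.

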#### **E. Provide a brief summary of the purpose of the research in non-technical language.**

Although it is widely known that increased exercise in older age improves cognitive, affective and physical wellbeing, many older Americans are sedentary. Developing and understanding techniques that motivate older adults to engage in physical activity has the potential to impact a spectrum of health-related behaviors and to improve brain health and quality of life. Motivational processes change across the lifespan. Despite a decline in the neurobehavioral influence of motivation on learning, older adults demonstrate relatively preserved reward sensitivity compared to younger adults ([name] et al., 2018).

Converging evidence has shown that reflection about core values (self-affirmation) before exposure to health messages is associated with positive behavioral change in younger adults (Cohen & Sherman, 2014). This is thought to occur by highlighting the self-relevance of potentially threatening messages (Cascio et al., 2016). Human fMRI studies in younger adults have shown that self-affirmation before exposure to persuasive health messages increases physical activity and is associated with activation of medial prefrontal cortex and ventral striatum, brain systems that support self-referential processing and positive valuation (Cascio et

al., 2016; Falk et al., 2015). There is reason to think that self-affirmation would also be an effective strategy to promote physical activity in older adults: A key node in the brain network underlying self-referential processing, medial prefrontal cortex, is relatively spared in aging (Gutchess et al., 2007; Salat et al., 2004).

We hypothesize that, (1) self-affirmation combined with gain-framed messaging will increase physical activity in older adults, while loss-framed messaging alone will not, (2) the added behavioral benefit from self-affirmation will be associated with increased activity in medial prefrontal cortex and ventral striatum, (3) individual differences in structural and functional frontosubcortical connectivity will predict change in physical activity. The overarching goals of this work are to identify and understand novel strategies to enhance physical activity in sedentary older adults and to characterize individual brain and neuropsychological differences that predict behavioral change. Our ultimate goal is to develop personalized behavioral interventions in older adults that tailor persuasive health-related messaging based on an individual's neurobehavioral profile.

